7. PHARMACOKINETICS AND PHARMACODYNAMICS ASSESSMENT

7.1 List of pharmacokinetic variables

To evaluate PK parameters of the drugs based on the data obtained on the concentration of anti-IL-6 receptor monoclonal antibody in the blood of volunteers, the following pharmacokinetic parameters will be calculated: the area under the "concentration-time" curve (AUC from the moment of administration of the drug to 1680 h (71 days after administration) and $AUC_{0-\infty}$ (to infinity), the maximum concentration of anti-IL-6 receptor monoclonal antibody in human serum, C_{max} , time to reach the maximum concentration, T_{max} , half-life, $T_{1/2}$, the elimination constant K_{el} and total clearance, CL, after a single-dose subcutaneous injection of the test drug. The values of the C_{max} and T_{max} will be calculated as the highest of the measured concentration values and the corresponding time of the observed maximum. The $AUC_{(0-t)}$ will be calculated using the logarithmic trapezoid method. The value of $AUC_{(0-\infty)}$ will be determined by the formula: $AUC_{(0-\infty)} = AUC_t + C_t/k_{el}$, where AUC_t is the area under the "concentration-time" curve from the moment of drug administration to the last measured BCD-089 concentration (in this study it is $AUC_{(0-1680h)}$), C_t and K_{el} are the calculated values of the drug concentration in the last sample (in this study – C_{1680h}) and the elimination constants, respectively. To calculate C_t and K_{el} , the final (monoexponential) section of the pharmacokinetic curve is described using nonlinear regression analysis.

Thus, the main PK parameters evaluated will include:

Primary:

- ✓ AUC_{0-1680} - area under the concentration-time curve from the administration of the drug to 1680 h (71 days after administration) and $AUC_{0-\infty}$ (to infinity).

Secondary:

- ✓ C_{max} (maximum serum concentration of anti-IL-6 receptor antibody);
- ✓ T_{max} (time to maximum concentration);
- ✓ $T_{1/2}$ (half-life),
- ✓ K_{el} (elimination rate constant),
- ✓ CL (total clearance).

Translated from Russian to English, dated 06-Jul-2020

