9. STATISTICAL METHODS

9.1 Calculation of the parameters of pharmacokinetics and pharmacodynamics

9.1.1. Pharmacokinetic parameters

Based on the calculated concentration values for the anti-IL-6 monoclonal antibody in the blood of each volunteer, the following pharmacokinetic variables will be estimated at time points specified in this protocol:

1. C_{\max} - maximum serum concentration of anti-IL-6 receptor antibody over the observation period.
2. t_{\max} - time to achieve maximum serum concentration (C_{\max}) of anti-IL-6 receptor antibody.
3. AUC_{0-1680} — the area under the concentration of anti-IL-6 receptor monoclonal antibody-time curve over the time interval from 0 to 1680 hours. AUC_{0-1680} will be calculated using the trapezoid method using the following formula, where C_p is the concentration of the drug BCD-089 in the blood at the time t_p in hours:

$$t_p \in \{0; 2; 8; 12; 24; 48; 72; 96; 120; 168; 240; 336; 504; 672; 1176; 1680\}_{p=1, \dots, 16}$$

4. $AUMC_{0-1680}$ - total area under the curve of the concentration of anti-IL-6 receptor monoclonal antibody multiplied by time over the time interval from 0 to 1680 hours. $AUMC_{0-1680}$ will be calculated using the following formula:

$$AUMC_{0-1680} = \sum_{p=2}^{16} \frac{(C_p * t_p + C_{p-1} * t_{p-1}) * (t_p - t_{p-1})}{2},$$

where C_p — concentration of anti – IL – 6

– receptor monoclonal antibody против рецептора ИЛ6

Translated from Russian to English, dated 06-Jul-2020

in the blood at t_p

$$t_p \in \{0; 2; 8; 12; 24; 48; 72; 96; 120; 168; 240; 336; 504; 672; 1176; 1680\}_{p=1, \dots, 16}$$

5. **Total clearance (Cl)** is a parameter that reflects the volume of test tissue, which is cleared from the anti-IL-6 receptor monoclonal antibody per unit of time and is determined by the ratio of the anti-IL-6 receptor monoclonal antibody dose (*DOSE*) to $AUC_{(0-1680)}$:

$$CL = \frac{DOSE}{AUC_{0-1680}}$$

6. **Mean residence time (MRT)** of the anti-IL-6 receptor monoclonal antibody molecule in the body will be calculated as the ratio of $AUMC_{0-1680}$ to AUC_{0-1680} :

$$MRT = \frac{AUMC_{0-1680}}{AUC_{0-1680}}$$

7. **Elimination constant** of the anti-IL-6 receptor monoclonal antibody (k_{el}) will be determined using the following formula:

$$k_{el} = \frac{1}{MRT}$$

8. **Half-life period** of the anti-IL-6 receptor monoclonal antibody ($T_{1/2}$) will be determined using the following formula:

$$T_{1/2} = \frac{\ln(2)}{k_{el}} = \ln(2) * MRT$$

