9.1.2. Pharmacodynamical parameters

Based on the obtained concentrations of C-reactive protein, IL-6 and soluble IL-6 receptor in the blood of each volunteer, the following pharmacodynamic parameters will be calculated at the Protocol-specified time intervals:

1. C_{\max} – maximum blood concentration of C-reactive protein, IL-6 and soluble IL-6 receptor over the observation period.
2. t_{\max} – time to maximum blood concentration (C_{\max}) of C-reactive protein, IL-6 and soluble IL-6 receptor.
3. AUC_{0-1680} – the area under the concentration-time curve for C-reactive protein, IL-6 and soluble IL-6 receptor over the time interval from 0 to 1680 hours. AUC_{0-1680} is calculated using the trapezoidal method with the following formula:

$$AUC_{0-1680} = \sum_{p=2}^{16} \frac{(C_p + C_{p-1}) * (t_p - t_{p-1})}{2},$$

where C_p concentration of C – reactive protein, IL – 6 and soluble IL
– 6 receptor values

ИЛ6 in the blood at t moment of time t_p (hours),

$$t_p \in \{0; 2; 8; 12; 24; 48; 72; 96; 120; 168; 240; 336; 504; 672; 1176; 1680\}_{p=1, \dots, 16}$$

4. C_{\min} – minimum blood concentration of C-reactive protein, IL-6 and soluble IL-6 receptor over the observation period.
5. t_{\min} – time to minimum blood concentration (C_{\min}) of C-reactive protein, IL-6 and soluble IL-6 receptor.

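### Sections 7 and 9 give different trapezoid rules for AUC0-1680, the primary PK and PD endpoint, and no visible text says which governs

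*Combined protocol and SAP*

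**What the plan says.** AUC0-1680, the "area under the concentration-time curve from the administration of the drug to 1680 h", is labelled primary for BCD-089 in Section 7.1, and for CRP, IL-6 and soluble IL-6 receptor in Section 7.2. The synopsis agrees.

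- **Sections 7.1 and 7.2.** AUC(0-t) "will be calculated using the logarithmic trapezoid method"; the sentence is the same in both. Each section then identifies the area to the last sample with AUC0-1680 in this study, so the sentence does govern the primary endpoint.
- **Section 9.1.1 (PK).** AUC0-1680 "will be calculated using the trapezoid method using the following formula". The AUC formula itself does not appear in the available text. The AUMC formula in the same list, on the same time grid, is a linear trapezoid.
- **Section 9.1.2 (PD).** AUC0-1680 "is calculated using the trapezoidal method with the following formula", and the formula is visible: the sum of (C_p + C_{p-1})(t_p − t_{p-1})/2, which is the linear trapezoid.

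The Section 9 formulas take t_p from a fixed list of hours: "0; 2; 8; 12; 24; 48; 72; 96; 120; 168; 240; 336; 504; 672; 1176; 1680". Section 9.1.1 derives CL and MRT from AUC0-1680, k_el and T1/2 from MRT, and AUC0-∞ from AUC0-1680 and k_el.

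**The concern.** The logarithmic and linear trapezoids are different estimators and give different areas from the same concentrations. An analyst who follows Section 7 and one who follows Section 9 will report different primary results, and both can claim to have followed the plan. Section 9.3 places the analysis after the last volunteer's data are in, and the study is open-label, so the choice would be made with the data in hand.

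The difference also passes into CL, MRT, k_el, T1/2 and AUC0-∞ through the Section 9.1.1 formulas. For PD, most cohorts may hold only three volunteers, so one volunteer with an intercurrent rise in CRP or IL-6 can move a cohort summary by an amount that depends on the rule.

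A second, smaller difficulty is that a purely logarithmic rule has no value on an interval that starts at zero. BCD-089 had never been given to humans (Section 1.4), and earlier antibody treatment against IL-6 or its receptor is excluded, so the expected pre-dose drug level is zero.

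**Working it through.** The plan gives no figure to reproduce. The check is to run both rules on the plan's own grid.

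**Rules, for an interval of length Δ with end concentrations C1 and C2**
- Linear: (C1 + C2)Δ/2
- Logarithmic: (C2 − C1)Δ/ln(C2/C1), with limit C1·Δ when C1 = C2
- Linear-up/log-down: linear when the concentration rises or an end value is zero, otherwise logarithmic

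For one interval the ratio linear/logarithmic is 1.04, 1.16, 1.34 and 1.57 for a 2-, 4-, 8- and 16-fold fall. The gap therefore arises mainly in long intervals with a large fall. The last two intervals, 672 to 1176 h and 1176 to 1680 h, are each 504 h.

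**PK (assumed profiles).** The shape is C(t) = ka/(ka − k)·(e^(−kt) − e^(−ka·t)), with k = ln 2/half-life, ka = ln 2/absorption half-life and C(0) = 0. The logarithmic column uses a linear step on 0 to 2 h so that it can be run at all.

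| Half-life / absorption half-life (h) | True area | Linear | Logarithmic | Linear vs true | Linear vs log |
|---|---|---|---|---|---|
| 72 / 24 | 103.9 | 106.0 | 102.7 | +2.0% | +3.2% |
| 150 / 48 | 216.3 | 223.8 | 214.6 | +3.5% | +4.3% |
| 168 / 48 | 242.0 | 250.6 | 240.4 | +3.5% | +4.2% |
| 336 / 24 | 468.4 | 479.1 | 467.1 | +2.3% | +2.6% |
| 500 / 24 | 647.5 | 656.6 | 646.2 | +1.4% | +1.6% |

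For half-lives from 50 to 500 h and absorption half-lives of 24 and 48 h, linear exceeds the true area by 1.4% to 3.5% and exceeds logarithmic by 1.6% to 4.3%. Linear-up/log-down lies 0.2% to 1.2% below the true area. Since CL is dose/AUC, a 4.3% larger area gives a CL lower by 1 − 1/1.043 = 4.1%.

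**The 0 to 2 h interval.** With C(0) = 0 the logarithmic rule is undefined. Replacing zero by a small number does not settle it: for C(2 h) = 1 the area is 0.43, 0.22 or 0.11 when zero becomes 10⁻², 10⁻⁴ or 10⁻⁸, against about 1.0 by the linear rule. The interval is at most about 0.08% of AUC0-1680 on these profiles.

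**PD, smooth curves (assumed).** A CRP dip, 1 − 0.9·exp(−((t − 240)/300)²), gives 1245.0 linear and 1235.7 logarithmic, a gap of 0.8%. A receptor rise, 1 + 4(e^(−t/500) − e^(−t/60)), gives 3408.8 and 3392.1, a gap of 0.5%.

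**PD, one isolated rise (assumed).** Take a level of 1 throughout and a single value h at one sampling time. Let D be the combined length of the two intervals that meet there. Then linear = 1680 + (h − 1)D/2, and logarithmic = 1680 − D + D(h − 1)/ln h. For h = 5 at 672 h, D = 168 + 504 = 672, so linear = 1680 + 4 × 336 = 3024, logarithmic = 1008 + 672 × 4/1.609 = 2678, and the gap is 12.9%. Excess of linear over logarithmic:

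| h | 168 h (D = 120) | 336 h (D = 264) | 672 h (D = 672) | 1176 h (D = 1008) |
|---|---|---|---|---|
| 3 | 1.2% | 2.5% | 5.4% | 7.2% |
| 5 | 3.3% | 6.6% | 12.9% | 16.3% |
| 10 | 9.4% | 17.2% | 29.4% | 34.8% |

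**MRT = AUMC/AUC.** At an assumed 100 h half-life, using the linear rule for both areas puts MRT 1.4% to 1.5% above its true value over 0 to 1680 h. Changing AUC alone to linear-up/log-down and leaving AUMC linear raises that to 4.8% to 5.3%. Changing both keeps the error within about 0.7% on all the assumed profiles.

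**The case against.** - **The PK conflict rests on an inference.** This stands as a caveat. Section 9.1.1 does not say linear, and its AUC formula is not visible. A reader might treat the PK contradiction as being as explicit as the PD one; the text does not go that far. The inference is still strong: the word logarithmic is absent, and the adjacent AUMC is linear on the same grid.
- **Logarithmic may be shorthand for linear-up/log-down.** Possibly, and that would remove the zero problem. Section 7 does not say so, and the conflict with the formula in Section 9.1.2 would remain.
- **The primary endpoint can still be computed.** Agreed. A reader might infer that the Section 7 rule makes AUC0-1680 impossible to calculate. One linear step on a negligible interval is enough, and Section 9.5 on missing and non-evaluable data is redacted and may already provide it. CRP, IL-6 and sIL-6R are endogenous, so a zero baseline is not the expected case for them.
- **The PK gap is small for a descriptive study analysed with rank tests.** Also fair. A shift of a few percent in one direction will rarely reorder volunteers. It does change the reported AUC and CL.
- **Large PD gaps come from chosen scenarios.** True. A 20-fold value at 672 h gives 8064 against 5270, a gap of 53%, from which a reader might infer that the rule dominates the PD result. The same rise at 24 h gives 8%, and smooth curves differ by under 1%. The documents do not show how often such rises will occur.
- **Agreement matters more than which rule is chosen.** Correct. The choice in the fix is a recommendation; the need to reconcile the sections is not.

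**Conclusion.** The contradiction is explicit for PD (Section 7.2 against 9.1.2) and well supported by inference for PK (Section 7.1 against 9.1.1). It concerns the primary endpoint, and nothing visible gives precedence to either section.

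The PK effect is modest, and its size depends on the one-compartment assumption. The PD effect is negligible for smooth curves and material only where a volunteer has an isolated late rise; the table above depends wholly on the height and timing assumed. Any carry-over into k_el and T1/2 applies to the Section 9.1.1 route through MRT. The point should be corrected before analysis. It does not invalidate the endpoint, and the documents do not support calling the log rule unworkable or the plan silent on zero values.

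**What to change.** State one rule per analyte, in the same words in Sections 7 and 9.

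- **BCD-089 (7.1 and 9.1.1):** linear-up/log-down, with the pre-dose concentration set to 0. Apply it to AUC and AUMC together, so that MRT does not mix rules. On a log-down interval with k = ln(C1/C2)/Δ, the AUMC contribution is (t1·C1 − t2·C2)/k + (C1 − C2)/k². Replace the logarithmic sentence in 7.1 and both formulas in 9.1.1.
- **CRP, IL-6 and sIL-6R (7.2 and 9.1.2):** keep the linear formula of 9.1.2 and delete the logarithmic sentence in 7.2.
- **Zero and below-quantification values:** state the handling beside the rule, or refer to Section 9.5 if it is there.
- **Times:** define t_p as actual elapsed time since dosing. Section 6.6 already checks sampling against allowed windows; the fixed list can remain as the nominal schedule.

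The cost is wording and minor programming. No sample, visit or volunteer is added.

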9. **The area under the concentration-time curve** for anti-IL-6 receptor monoclonal antibody **over the time interval from 0 to ∞ ($AUC_{0-\infty}$)**.

$$AUC_{0-\infty} = AUC_{0-1680} + \frac{C_{1680}}{k_{el}}, \text{ where}$$

Translated from Russian to English, dated 06-Jul-2020

C_{1680} – concentration of anti-IL-6 receptor antibody over the period equal to 1680 hours after the drug administration.

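### Sections 7.1 and 9.1.1 define AUC0-inf, a primary PK endpoint, in two different ways, and both extrapolate every volunteer from 1680 h, which can bias it at the lowest doses

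*Combined protocol and SAP*

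**What the plan says.** The synopsis and section 7.1 list AUC0-inf with AUC0-1680 as primary pharmacokinetic endpoints. The calculation is then given twice.

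- **Area rule.** In 7.1 the area "will be calculated using the logarithmic trapezoid method". In 9.1.1 it "will be calculated using the trapezoid method using the following formula"; the PK formula itself is not in the public text, but the AUMC formula beside it and the AUC formula in 9.1.2 are linear.
- **Last concentration.** In 7.1, C_t and k_el "are the calculated values of the drug concentration in the last sample" and the elimination constant, and to obtain them "the final (monoexponential) section of the pharmacokinetic curve is described using nonlinear regression analysis". In 9.1.1 item 9 the term is the "concentration of anti-IL-6 receptor antibody over the period equal to 1680 hours after the drug administration", with no fit mentioned.
- **Elimination constant.** It is a terminal regression in 7.1. In 9.1.1 it is 1/MRT, with MRT = AUMC0-1680/AUC0-1680.
- **Extrapolation point.** In 7.1 the area runs "from the moment of drug administration to the last measured BCD-089 concentration (in this study it is" the 0-1680 h area). Section 9.1.1 adds C1680/k_el to AUC0-1680. Neither gives a last quantifiable time per volunteer.

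The text of 4.6.3.6.1 (BCD-089 assay) and 9.5 (missing, non-evaluable and uncertain data) is redacted.

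**The concern.** Two analysts following the two sections would report different values of the same primary endpoint from the same samples.

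The shared 1680 h point is a separate matter. Once a volunteer's drug falls below the assay limit, there is no measured concentration at 1680 h to extrapolate from. Under 9.1.1 the tail then becomes whatever value is substituted. Under 7.1 the fit still returns a positive C_t, but the gap from the last quantifiable sample to 1680 h has no defined area. A logarithmic trapezoid cannot be evaluated on an interval with a zero at one end, which already affects the first interval from time 0 if the pre-dose value is zero.

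Low doses lose signal first, so any error would vary with dose, and exposure by dose is what an escalation study describes.

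**Working it through.** The plan states no extrapolated share and no expected error, so there is no figure of its own to reproduce.

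**1. Inputs from the documents.** Doses 0.06 to 2.9 mg/kg; sampling at 0, 2, 8, 12, 24, 48, 72, 96, 120, 168, 240, 336, 504, 672, 1176 and 1680 h (9.1.1). The last two intervals are 504 h each.

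**2. When signal is lost.** The dose ratio is 2.9/0.06 = 48.3. Under linear kinetics the lead time to any fixed limit is log2 of the dose ratio: log2(48.3) = 5.6 half-lives for 0.06 mg/kg and log2(2.9/0.3) = 3.3 for 0.3 mg/kg. This needs no assumed half-life or limit.

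**3. Size, under assumptions.** None of the following is in the documents: one compartment, 75 kg, V/F 8.6 L, absorption half-life 48 or 60 h, elimination half-life 7 or 14 days, limit 0.02 to 0.2 ug/mL, no noise, unquantifiable values set to 0.

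- Fixed point (9.1.1 form): linear AUC0-1680 + C1680/k, with the true k so that only the 1680 h rule acts.
- Own last sample: AUC0-tlast (linear up, log down) + C_tlast/slope, slope from the last three quantifiable points.

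*One case by hand* (0.06 mg/kg, half-lives 168 h and 48 h, limit 0.1):
- Dose 0.06 × 75 = 4.5 mg; k = ln2/168 = 0.004126 per h; true AUC0-inf = 4.5/(8.6 × 0.004126) = 126.8 ug·h/mL.
- Concentrations are 0.177 at 336 h and 0.091 at 504 h, so 336 h is the last quantifiable sample.
- True area after 336 h is 44.0. The rule draws a triangle, 0.177 × 168/2 = 14.9, and adds no tail. The shortfall is 29.1/126.8 = 23%. Linear-trapezoid error before 336 h brings the total to -24.0%.

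Error in AUC0-inf at 0.06 mg/kg:

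| Absorption / elimination half-life | Limit (ug/mL) | Last quantifiable (h) | Fixed 1680 h | Own last sample | Extrapolated share |
|---|---|---|---|---|---|
| 48 h / 7 d | 0.02 | 672 | +0.9% | -0.4% | 9% |
| 48 h / 7 d | 0.1 | 336 | -24.0% | +8.1% | 41% |
| 48 h / 7 d | 0.2 | 240 | -44.5% | +41.7% | 68% |
| 48 h / 14 d | 0.1 | 672 | -14.4% | 0.0% | 30% |
| 48 h / 14 d | 0.2 | 504 | -35.7% | +2.1% | 44% |
| 60 h / 7 d | 0.1 | 336 | -26.4% | +16.7% | 48% |
| 60 h / 7 d | 0.2 | 240 | -47.5% | +93.4% | 78% |
| 60 h / 14 d | 0.2 | 504 | -37.0% | +7.1% | 48% |

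At 0.3 mg/kg and above, over all these settings, the fixed point gives -3.5% to +3.7% and the own-last-sample rule -0.6% to -0.1%.

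**4. Saturable elimination** (two assumed Vmax/Km pairs, limit 0.01 to 0.5 ug/mL, zeros). The fixed point gives -33% at worst at 0.06 mg/kg, -17% at worst at 0.3 mg/kg and above, and up to +5% at 2.9 mg/kg. In some settings the lowest doses have no quantifiable sample at all.

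**5. Dependence on the substitution rule.** In a second linear grid (half-lives 3 to 21 days, limit 0.1% to 10% of Cmax, signal lost before 1680 h), the 9.1.1 form gives -4.0% to +3.3% with zeros but 0% to +44% with half the limit. The 7.1 form gives -11.2% to -0.7% if the gap to 1680 h is left out.

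**6. The k_el conflict.** After subcutaneous dosing, MRT includes absorption time. Without truncation, (1/MRT)/k = elimination half-life/(elimination + absorption half-life) = 168/(168 + 48) = 0.78. So 9.1.1 would report a half-life of 216 h where the terminal one is 168 h. At a 21-day half-life, cutting AUMC at 1680 h reverses this, to a ratio of 1.25.

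**The case against.** The strongest reply is that no bias has been shown. Its size and sign rest on an assay limit and a rule for unquantifiable values that sit in redacted text. Setting them to zero is my assumption, and step 5 shows the sign changing with the rule. That stands. A reader might infer that the plan has no such rule, or that AUC0-inf is biased as planned; the public text supports neither.

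Second, section 7.1 speaks of the last measured concentration, so its 1680 h note may describe only the nominal case. That is possible, but 9.1.1 fixes 1680 h in the formula without any such wording. The straight line to zero in step 3 is also a reading of 9.1.1 only; 7.1 as written would not produce it.

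Third, the large linear-case errors fall on one person. Cohort 01 is a single volunteer with no expansion, and from 0.3 mg/kg the errors are a few percent. The visible analysis is descriptive summaries and general rank tests, with no dose-proportionality model. So the inference that exposure across doses is distorted, or that spurious non-linearity would appear, is not shown under linear kinetics.

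Fourth, the remedy can do worse than the plan. In the case where the fixed point gives -47.5%, extrapolating from the volunteer's own last sample gives +93.4%, because the slope comes from samples still affected by absorption. That is correct, and it is why the remedy needs a limit on the extrapolated share.

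Finally, a reader might take the fitted versus unfitted C_t as the cause of the low-dose error. It is not. It is a separate inconsistency; the error comes from the fixed point together with the substitution rule.

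**Conclusion.** The point holds as an inconsistency and a conditional risk. Without any assumption, 7.1 and 9.1.1 disagree on the trapezoid rule, on C_t and on k_el for a primary endpoint, and both place the extrapolation at 1680 h for every volunteer over a 48-fold dose range.

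Whether AUC0-inf is materially wrong cannot be settled from the public text. Under assumed linear kinetics with zeros, the error is about +1% to -47% for the one 0.06 mg/kg volunteer and within about 5% from 0.3 mg/kg up. With assumed saturable elimination it reached -17% in the cohorts from 0.3 mg/kg. These are illustrations, not predictions for BCD-089.

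It should be corrected before analysis. Confidence is high on the conflict and moderate on its practical effect.

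**What to change.** In 7.1 and in 9.1.1 items 3, 7 and 9, state one definition:

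- AUC0-inf = AUC0-tlast + C_tlast/k_el, with tlast each volunteer's last quantifiable sample.
- k_el from the terminal regression, not 1/MRT, and T1/2 from the same k_el.
- One trapezoid rule that can be evaluated on the first interval and on rising concentrations.
- One stated choice of observed or fitted C_tlast.

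Check this against the rule for unquantifiable values in 9.5. Report the extrapolated percentage for each volunteer, and do not summarise AUC0-inf above a pre-stated limit. A limit of 20-30% is a convention offered as an example. In the step 3 model the own-last-sample error was at most about 1% up to a 32% share, +2% to +17% at 41-48%, and +42% to +93% at 68-78%.

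Keep AUC0-1680 as a separate quantity. While editing, reconcile its label: 1680/24 = 70 days after injection, which is the Day 71 visit, not 71 days after administration.

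The cost is protocol or SAP wording only, with no new samples or visits. The downside is that AUC0-inf may go unreported for the lowest-dose volunteers.

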1.3.2. Clinical studies of the test drug

Not performed.

1.4. Summary of known and potential risks and benefits for clinical trial subjects (risk/benefit ratio)

Benefit evaluation

BCD-089 is an innovative drug, which has never been used in humans. The first stage of BCD-089 clinical development will be to evaluate its effects in healthy volunteers, which means that participants in such a study will not derive subjective (personal) benefits from their participation in it, except for a detailed medical examination; however, data obtained after the completion of this study will have high scientific value and may help introduce into clinical practice a new highly effective product for the treatment of severe autoimmune disorders.

Risk evaluation

[REDACTED]

Translated from Russian to English, dated 06-Jul-2020

[Redacted content]

Translated from Russian to English, dated 06-Jul-2020

[Redacted content]

Translated from Russian to English, dated 06-Jul-2020

1.5. Description and justification of the study design, the method of administration of the test drug, dose, dosing regimen and the course of treatment

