4.6.3.6. Determination of BCD-089, IL-6 receptor, C-reactive protein, IL-6 concentrations

4.6.3.6.1 Determination of BCD-089 concentrations

[Redacted text block]

Table 10. [Redacted]

[Redacted]	[Redacted]

[Redacted text block]

Translated from Russian to English, dated 06-Jul-2020

[REDACTED]

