9.2 Statistical analysis methods

The study results will be analyzed using the two-sided statistical hypotheses with a significance level of 0.05.

Translated from Russian to English, dated 06-Jul-2020

Quantitative and scale data

To describe quantitative and scale variables, it is planned to use the following characteristics: mean, median, standard deviation, quartiles, minimum and maximum, and coefficient of variance.

The statistical analysis of the obtained data will be conducted using SAS 10.0 software and the R programming language for statistical data processing. Mann-Whitney, Wilcoxon, Kruskal-Wallis, and Friedman tests will be used to compare quantitative and scaled data. The categorical data will be processed using the Fisher's exact test and the χ^2 Pearson test.

Quantitative data include the following parameters:

- Membrane receptor occupancy with BCD-089

Pharmacokinetics:

- Anti-human interleukin-6 receptor monoclonal antibody concentration
- Area under the curve
- Time (including time to maximum concentration, half-life period)
- Elimination characteristics (clearance, elimination constant)

Pharmacodynamics:

- Human IIL-6, C-Reactive Protein, soluble IL-6 receptor concentrations
- Area under the curve
- Time (including time to maximum concentration, trough concentration, time to achieve trough concentration)
- Elimination characteristics (clearance, elimination constant)

Tenderness:

Value specified in Visual Analogue Scale (out of 10 points)

Safety:

- Complete blood count parameters
- Blood biochemistry parameters
- ECG parameters
- Urinalysis parameters

Translated from Russian to English, dated 06-Jul-2020

- Blood pressure, wrist pulse rate and body temperature
- Size of an abnormal lesion at the injection site reactions
- Time of presence of the abnormal lesion at the injection site

Categorical data include the following parameters:

Pharmacodynamics:

- Proportion of samples showing the maximum signal for membrane IL-6 receptor occupancy

Safety:

- Nature of an abnormal lesion at the injection site
- Frequency of AEs and SAEs by severity grades
- Frequency of grade 3/4 toxicity events
- Frequency of injection-site reactions (total and depending on the type of the lesion)
- Proportion of subjects who developed any grade neutropenia in each cohort.
- Frequency of cases of premature discontinuation from the study due to an AE/SAE

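### Section 7.1 leaves the terminal fit for C_t and K_el unspecified; run in the default way, it would usually give a less precise K_el than a log-linear fit of the same samples

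*Combined protocol and SAP*

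**What the plan says.** Section 7.1 forms AUC0-inf as the area to the last sample plus C_t/k_el. For C_t and K_el it states that "the final (monoexponential) section of the pharmacokinetic curve is described using nonlinear regression analysis", and the two quantities "are the calculated values of the drug concentration in the last sample" and the elimination constant, so C_t is a fitted value there. That is the whole description of the fit in the readable text. Section 7.1 lists AUC0-inf as primary and K_el and T1/2 as secondary, and gives no formula for T1/2.

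Section 9.1.1 gives the sampling hours, "0; 2; 8; 12; 24; 48; 72; 96; 120; 168; 240; 336; 504; 672; 1176; 1680", and defines the same parameters another way: k_el = 1/MRT with MRT = AUMC0-1680/AUC0-1680, and T1/2 = ln(2) × MRT. Its tail term uses C_1680, described as the "concentration of anti-IL-6 receptor antibody over the period equal to 1680 hours after the drug administration", which reads as the measured value. No regression appears there.

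The sample-size section plans three volunteers per cohort from cohort 02 on, rising to six only after a DLT. The assay text (4.6.3.6.1) and the section on missing and non-evaluable data (9.5) are redacted.

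**The concern.** A monoexponential is a straight line on the log scale, so calling the regression nonlinear points to a fit on untransformed concentrations. With no weights named, ordinary least squares is what most software will do. It minimises absolute residuals, while concentrations over the late samples fall several-fold to several tens-fold. The first, highest sample then largely sets the slope, and the 1176 h and 1680 h samples, whose long time lever makes them most informative about the slope, have little influence. If assay error is roughly a constant percentage of concentration, that wastes information.

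At stake is the precision of K_el in each volunteer. With three volunteers in most cohorts, averaging removes little of this noise, and it can hide or mimic a change of elimination with dose. The open choice of weights and window also leaves an analyst decision to be made after the data are seen, in an open-label study.

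**Working it through.** The documents state no precision for k_el or T1/2, so there is no figure to reproduce.

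**Inputs.** Sampling hours come from 9.1.1. The human half-life is unknown ("BCD-089 is an innovative drug, which has never been used in humans") and the assay error is not visible. Half-life, CV, additive error and quantification limit are therefore assumptions, varied below.

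**Formulas, constant CV.** Let c_i be the concentration relative to the first terminal sample, w_i = c_i², and d_i = t_i minus the w-weighted mean time. To first order:

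- unweighted nonlinear fit: SE(k) = CV × √(Σw²d²) / Σwd²
- log-linear fit: SE(k) = CV / √(Σ(t − t̄)²)

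SE(k)/k approximates the SD of ln(K_el).

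**Worked case: 336, 504, 672, 1176 and 1680 h, half-life 16 days (384 h), CV 10%.** k = ln(2)/384 = 0.001805 per h.

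- c = 1, 0.738, 0.545, 0.220, 0.088; w = 1, 0.545, 0.297, 0.048, 0.0078
- weighted mean time 463.7 h; d = −127.7, 40.3, 208.3, 712.3, 1216.3
- Σwd² = 66,102; Σw²d² = 21,897
- nonlinear: SE = 0.1 × 148.0/66,102 = 0.000224; SE/k = 0.124
- log-linear: t̄ = 873.6, Σ(t − t̄)² = 1,207,987; SE = 0.1/1,099 = 0.0000910; SE/k = 0.050
- ratio 2.46

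In the nonlinear fit the 336 h sample alone supplies 127.7²/21,897 = 74% of the variance of k.

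**Same window, other half-lives (CV 10%).**

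| Half-life (days) | First/last concentration | First sample's share of Σc² | SE/k nonlinear | SE/k log-linear | Ratio | Simulated ratio |
|---|---|---|---|---|---|---|
| 10 | 48.5 | 0.65 | 0.134 | 0.031 | 4.27 | 4.20 |
| 16 | 11.3 | 0.53 | 0.124 | 0.050 | 2.46 | 2.44 |
| 21 | 6.3 | 0.47 | 0.118 | 0.066 | 1.79 | 1.82 |
| 28 | 4.0 | 0.41 | 0.123 | 0.088 | 1.40 | not run |

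**Whole-profile simulation.** Assumptions: one-compartment subcutaneous model, 75 kg, V/F 8.6 L, absorption half-life 2 days, half-life 7–21 days, CV 10–20%, additive error 0 or 0.03 µg/mL, quantification limit 0.1 µg/mL, doses 0.3, 1.0 and 2.9 mg/kg, windows from 336 or 504 h. In 88 evaluable cells the ratio of SDs ran from 0.96 to 4.19, and 87 cells were at 1.16 or above. The cell below 1 was 0.3 mg/kg, 7 days, with additive error. There the dose is 22.5 mg and 22.5/8.6 = 2.6 µg/mL; after seven half-lives (1176 h) only a few hundredths of a µg/mL remain, below the assumed limit. About three samples (336, 504, 672 h) survive and the two methods nearly agree.

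**Outside these assumptions.** With purely proportional error and no quantification limit, half-lives of 4–8 days and windows to 1680 h give 1.86 to 11.8. Windows ending at 672 h give 1.02 to 2.9. Now add a constant error of 3% of the first terminal concentration to the worked case:

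- nonlinear: variance (0.01 × 21,897 + 0.0009 × 66,102)/66,102² = 6.37 × 10⁻⁸
- log-linear: Σ(t − t̄)²/c² = 85.8 million, so variance (0.01 × 1,207,987 + 0.0009 × 85.8 million)/1,207,987² = 6.12 × 10⁻⁸
- ratio √(6.37/6.12) = 1.02

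The same formulas at 13 days give 0.79, so the log-linear fit can be the worse one. These additive-error figures are first-order and unreliable where the last concentrations approach the additive error.

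**AUC0-inf.** Ignoring absorption, the tail is 2^(−1680/384) = 4.8% of the total at 16 days. An error in k changes the tail C_t/k by a factor of about 1 + k × (1680 − centre of fit) times the relative error in k. Nonlinear: (1 + 0.001805 × 1216.3) × 0.124 × 0.048 = 1.9% of AUC0-inf. Log-linear: (1 + 0.001805 × 806.4) × 0.050 × 0.048 = 0.6%. Both double at CV 20%.

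**Cohort of three.** Assume a between-volunteer SD of ln(K_el) of 0.25. In the worked case total variance rises by (0.0625 + 0.0154)/(0.0625 + 0.0025) = 1.20, so three volunteers inform like 3/1.20 = 2.5. At CV 20% the simulated fitting SDs are 0.253 and 0.103: (0.0625 + 0.0640)/(0.0625 + 0.0106) = 1.73, and 3/1.73 = 1.7.

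**The case against.** The strongest reply is that 7.1 is silent rather than wrong: a 1/C²-weighted nonlinear fit, which performs like the log-linear one, is already compatible with its sentence, and a rule on evaluable samples could sit in the redacted 9.5. That stands as far as it goes. A reader might infer that the plan prescribes an unweighted fit; it does not. But a method sentence that allows fits of such different efficiency, with the less efficient one as the usual default, is worth closing.

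Second, a reader might infer that the half-life endpoint is 1.2 to 4 times less precise. The documents do not support that as they stand: the only T1/2 formula is ln(2) × MRT in 9.1.1, where no regression enters. The same applies to K_el and the AUC0-inf tail if 9.1.1 governs. This limits the point to K_el and C_t under 7.1, and to T1/2 once the two sections are aligned that way.

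Third, every input to the factor is assumed, and ratios from below 1 to about 12 can be produced. That is correct, and the factor must be quoted with its conditions.

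Two further extensions are tempting. Section 7.2 repeats the sentence for CRP, IL-6 and soluble receptor, but the calculations cover drug concentration only, and neither k_el nor T1/2 is a listed PD endpoint in 7.2. Nor is there any figure showing that leftover absorption at the first terminal sample does damage here.

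**Conclusion.** The point holds as a conditional one. Section 7.1 does not state the weighting, scale or sample selection of the fit that yields C_t and K_el. Run unweighted on raw concentrations with roughly proportional error, it would usually give a less precise K_el than a log-linear fit. The SD of ln(K_el) would be about 1.2 to 4 times larger under the assumed half-lives of 7–21 days, CV of 10–20%, small additive error, quantification limit of 0.1 µg/mL and samples from 336 h. The advantage shrinks to nothing, or reverses, when additive error is large relative to the late concentrations. The consequence for the primary AUC0-inf is a few percent at most. Nothing follows for T1/2 unless it is taken from this K_el, which 9.1.1 at present does not do. The change is worth making because it is cheap and removes a post-hoc choice, not because a primary result is in danger.

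**What to change.** In 7.1, replace the sentence on the terminal fit with: k_el is minus the slope of the linear regression of ln(concentration) on time over the quantifiable terminal samples after Cmax, with at least three such samples (or nonlinear regression weighted by 1/C²); C_t is the value predicted by that fit at the last sample. Name one of the two options, ideally after looking at the assay's validated error profile, and write down before analysis how the first sample of the terminal section is chosen.

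Align 9.1.1 in the same amendment, so that this one k_el is used for K_el, for T1/2 = ln(2)/k_el and for the AUC0-inf tail, with the same C_t. Changing 7.1 alone would leave the MRT-based definitions in force.

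The cost is a sentence in 7.1 and matching edits in 9.1.1, with the same samples and standard software. The downside is that a volunteer with fewer than three quantifiable terminal samples has no reported K_el or T1/2, which is most likely at the lowest doses.
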